Sample size: At a refractive error prevalence of 3%, with minimum of 300 children/school, 95% of children receiving spectacles in the School Model, 40% of children wearing them in both the School Model and Referral Model groups at un-announced 3 month visits, a cost of US\$1.30 per child screened in the School Model and US\$0.80 in the Referral Model (all assumptions based on REACH Program data), if 58.5% of families accept referral to receive refraction and spectacles in the Referral Model, this would reach the same cost-effectiveness as the School Model. A total of 141 schools (47 in each of three groups) across three participating hospitals would be sufficient to detect significantly better cost-effectiveness of the Referral Model if 65% of families accept referral for refraction/spectacles, which is the target in our hypothesis; with a power of 90%, an alpha-error of 0.05, and an intracluster correlation coefficient (ICC) (a measure of how similar children are to one another within schools: "clustering") of 0.20.

Randomization: An independent statistician having no contact with participants will generate the randomization sequence using a computer system that is inaccessible until after the school has agreed to join the trial. Schools will be stratified into two groups as Public and private. The schools in each stratified group will be randomly assigned to either the intervention (referral models) or control group (school model) in a 1:1:1 ratio with a block size of three to ensure balance. After randomization, the schools and the children in them will not be masked to their allocated intervention but staff assessing data for the main outcome will not know a child's group assignment.

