Referral Model (47 schools): Vision screening carried out by the vision screeners; and children are referred to nearby Vision Center/ secondary center for refraction and delivery of free spectacles. Teachers will contact families not presenting for follow-up care and for spectacle compliance through SMS, phone call and notations in the school diary.

Referral Model + Cost Recovery (47 schools): Vision screening carried out by the vision screeners; children referred to Vision Center for refraction and delivery of spectacles with an option to purchase "upgrade spectacles" (which was shown to be appealing to families in the recent PRICE study[14]. These spectacles have scratchproof coatings and designs selected to appeal to local children. Teachers will contact families not presenting for follow-up care through SMS, phone call and notations in school diary.

Number of Arms: 3

Masking: Single (Investigator) : Investigators assessing the components of the main study outcome will be masked to the study group assignment of the school.

Staff assessing data for the main outcome will be masked to a child's group assignment.

Allocation: Randomized

Enrollment: 141 schools [Anticipated]

Arms and Interventions

Experimental: School Model

Vision screening will be carried out by the vision screeners; refraction will be done at the schools by refractionists; and children who need them will be given free spectacles at the school within two weeks.

Experimental: Referral Model

Referral Model (47 schools): Vision screening carried out by the vision screeners; and children are referred to nearby Vision Center/ secondary center for refraction and delivery of free spectacles. Teachers will contact families not presenting for follow-up care and for spectacle compliance through SMS, phone call and notations in the school diary.

Experimental: Referral Model + Cost Recovery

Referral Model + Cost Recovery (47 schools): Vision screening carried out by the vision screeners; children referred to Vision Center for refraction and delivery of spectacles with an option to purchase "upgrade spectacles" (which was shown to be appealing to families in the recent PRICE study[14]. These spectacles have scratchproof coatings and designs selected to appeal to local children. Teachers will contact families not presenting for follow-up care and for spectacle compliance through SMS, phone call and notations in school diary.

Outcome Measures

Primary Outcome Measure:

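### With a fixed, published block of three and open allocation, the last school of each block can be deduced in advance if schools are randomised one at a time

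*Combined protocol and SAP*

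**What the plan says.** The Randomization paragraph gives a concrete method. The list is produced by a statistician who is independent of the trial and does not meet participants. On concealment, this is done "using a computer system that is inaccessible until after the school has agreed to join the trial". On structure it says: "Schools will be stratified into two groups as Public and private". Within each stratum, schools are assigned 1:1:1 "with a block size of three to ensure balance". The design listing gives "Number of Arms: 3", so the block size equals the number of arms.

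The Sample size paragraph gives "A total of 141 schools (47 in each of three groups) across three participating hospitals". Hospital is not a stratification factor.

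On masking, the Randomization paragraph says that after allocation "the schools and the children in them will not be masked to their allocated intervention". The masking that is promised concerns outcome assessment: "staff assessing data for the main outcome will not know a child's group assignment". The Monitoring paragraph gives a project manager overall responsibility for planning and coordination, with a local assistant at each site. No masking to earlier allocations is stated for either role.

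The documents do not say whether schools are randomised singly or together, who decides which school is approached next, or whether the block size is withheld from recruiting staff.

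**The concern.** Concealing the sequence stops someone from reading the next entry. It does not stop someone from inferring it. When block size equals the number of arms and earlier allocations are visible, two known allocations in a block determine the third. Here the block size is also printed in the protocol.

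What is at stake is which school enters a predictable slot. A person who expects a Referral slot could, deliberately or not, put forward a school that is close to a Vision Center, well placed, or unusually motivated. None of these traits is stratified. The background section states that compliance with referral will be the most important determinant of the cost-effectiveness outcome. The Sample size paragraph puts break-even uptake at 58.5% and the target at 65%, so the primary hypothesis rests on a gap of 6.5 percentage points. That distance, location or motivation affects uptake is a plausible inference; the documents do not state it.

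**Working it through.** **Inputs.** Block size 3, ratio 1:1:1 and public/private strata (Randomization); three arms (design listing); 141 schools, 47 per arm (Sample size). Assumptions for the worst case: schools are allocated one at a time, and the guesser knows the block size and every earlier allocation in the stratum.

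**The plan's own figures.** 141 / 3 = 47 blocks with one school per arm in each, giving 47 per arm. This is exact if both strata are multiples of three. If they are not, the remainders are 1 and 2, and there are 46 complete blocks. The break-even uptake also reproduces: 0.95 × 0.80 / 1.30 = 0.585.

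**Predictability with a fixed block of three.**
- First school in a block: best guess correct with probability 1/3.
- Second school: 1/2.
- Third school: 1.
- Certain allocations: 1 in 3, that is 47 of 141 (46 if the strata are not multiples of three).
- Best-guess accuracy: (1/3 + 1/2 + 1) / 3 = 0.611, against 0.333 with no information.

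**School versus either Referral arm.** School is equally likely to be first, second or third in a block. If it is first, the next two must be Referral (2 certain). If second, the third must be Referral (1 certain). If third, that slot must be School (1 certain). The mean is (2 + 1 + 1) / 3 = 4/3 per block, so 47 × 4/3 ≈ 63 of 141 allocations (44.4%) are certain for this contrast.

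**A scale for the consequence, not an estimate.** The certain Referral-type slots average (2 + 1 + 0) / 3 = 1 of the 2 in each block, so half of the Referral slots are certain to be of Referral type. If every one of these were filled by a school whose uptake is d points higher than it would otherwise have been, mean Referral uptake would rise by d/2 (equal school sizes assumed). Moving it by the full 6.5 points would need d = 13. The documents give no figure for d, and the calculation leaves out slots that are guessable but not certain.

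**Alternatives, for the same fully informed guesser.** Fixed sizes were enumerated exactly. The varied blocks were simulated as one 141-school sequence with each size equally likely; the guesser knew the possible sizes but not the order in which they were used.

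| Scheme | Certain | Best-guess accuracy |
|---|---|---|
| Fixed 3 | 33.3% | 61.1% |
| Fixed 6 | 20.0% | 56.1% |
| Fixed 9 | 14.3% | 53.2% |
| Hidden, varied 3/6/9 | about 4.0% | about 55.4% |

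Under varied 3/6/9, 0.040 × 141 ≈ 6 schools are certain. If schools have all agreed before a single run, no arm can be deduced before agreement, whatever the block size.

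**The case against.** The strongest objection is that the plan never says schools are allocated one at a time. The concealment sentence speaks of the school in the singular, which suggests it, but the next sentences speak of the schools in each stratum being assigned, which fits a batch equally well. If a batch was intended, the problem does not arise. This stands, and it makes the point conditional.

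Three further objections limit the size. First, stratification is by sector and not by hospital. If one sequence runs across three hospitals, site staff who see only their own schools may be unable to deduce anything, although a central coordinator could. The 47 is therefore an upper limit for a fully informed person. Second, steering by public or private status would achieve little, because the blocks balance sector by design. Third, school and home distance to the nearest Vision Center and urban or rural location are baseline data, and the Data Analytic Plan compares outcomes with and without adjustment for such factors. That helps, but adjustment reaches only measured traits, so motivation is not covered, and an unadjusted comparison is also planned.

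A reader might infer that the arm of every third school approached is known beforehand. The documents do not support that. The deducible school is the last of each block within its stratum, and the deduction needs sequential allocation and sight of that stratum's earlier allocations.

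**Conclusion.** The point holds in conditional form. If schools are randomised one at a time, the fixed, published block of three lets a person with the right information deduce up to 47 of 141 allocations (46 if the strata are not multiples of three) before the school agrees, and guess correctly 61% of the time overall. The stated concealment does not address this.

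It rests on three assumptions: sequential allocation, knowledge of the block size together with the stratum's earlier allocations, and some discretion over which school is approached next. The documents exclude none of these and confirm only that the block size is published and allocation is open.

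It would go too far to conclude that selection bias has occurred, or that the comparison is invalid. Nothing in the documents shows steering, and the effect on uptake cannot be quantified from them. This is an inexpensive improvement to the protection against selection bias, not a fatal defect.

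**What to change.** State in the Randomization paragraph whether schools are allocated singly or in a batch, then do one of the following.

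- **If allocation is sequential:** replace the fixed block of three with randomly varied blocks of 3, 6 and 9 within each stratum, and do not disclose the sizes to recruiting or field staff. The main gain is in certain allocations (33% to about 4%); best-guess accuracy falls only from 61% to about 55%. The cost is a change to the randomisation program and slightly less exact balance. If a stratum ends inside a block of 9, two arms can differ by at most 3 schools in that stratum, or 6 over both strata in the worst case.
- **Alternatively:** randomise all schools in one run, or one run per hospital, after they have agreed. This removes the predictability entirely. It is not only a programming change: every school in the run must have agreed before any is allocated, which may delay the start for those that agree early.

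Neither option changes the planned number of schools, the interventions or the outcome definition.

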it will most likely be the more cost-effective model. If the teacher's intervention doesn't increase compliance in the Referral model, then the School model is likely to be the most cost-effective. Because money invested in school screening is wasted when families do not comply with referral to the Vision Centre in the Referral model, compliance with a referral will be the most important determinant of our main cost-effectiveness outcome.

Experimental plan Population: School children in the 6th to 10th grades (11-15 years of age) at public and private, rural and urban schools with a minimum of 300 students and covered by the Orbis India REACH (Refractive Error Among Children) program, including those located nearer and further from Vision Centers, which will serve as the principle eye care facilities in the study.

Eligibility: Enrolment criteria: Children in randomly-selected 6th to 10th grades in selected schools with presenting visual acuity (that is, wearing spectacles if spectacles are owned at baseline) \leq 6/9.6 (0.2 LogMAR) in either eye. Children who already own spectacles will be requested to bring their spectacles on the day of screening, and children whose vision with existing spectacles meets study criteria will be eligible. Exclusion criteria: Parents returning the form indicating they do not wish their child to participate; no Vision Center within 50 km of the child's home (a rare occurrence in the REACH network). If the child is incapable of completing visual acuity screening in both eyes for any reason.

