Data to be acquired at baseline: Child: Age, gender, spectacles ownership, presenting and best corrected visual acuity in both eyes; refractive error in both eyes; distance of child's home from nearest Vision Center; brief spectacle attitude questionnaire; brief family Socio-Economic Status (SES) questionnaire[15]. Teacher: Brief questionnaire on attitudes and knowledge towards spectacles. Program: Survey of all program costs for screening and distribution for each model. Our cost-effectiveness analysis will be from the Program rather than the societal perspective, but the investigators will capture travel cost info from a 1% sample of randomly-selected children/families and capture information about teacher time spent in meeting with parents, sending notes to parents and encouraging children to wear spectacles in a 1 % random sample of Referral group teachers, in order to perform a sensitivity analysis of the impact of including these costs. Regarding programs costs, in the School model, where the optometrist team does the screening at school, the program

cost will be calculated by taking the cost of the primary and secondary screening, cost of the spectacles, and cost of delivering them. In the Referral model, the investigators will include the cost of primary screening, secondary screening at the vision centres and the cost of spectacles. In the Cost recovery model, the cost recovered by selling the spectacles (difference between retail price and cost of spectacles to the hospital) will be subtracted from the program cost. School: Urban versus rural, public versus private, size of the school, SES of community, and distance of the school from nearest Vision Center.

[figure not shown]
Follow-up schedule and follow-up data: Self-reported and observed spectacle wear to be ascertained at an un-announced follow-up at school 3 months after distribution of spectacles. Additionally, the following data for the Referral groups will be collected from the referral centre and verified from the children in a random sample of 10% of children: Did they visit the referral centre? Did they receive free spectacles? Did they elect to purchase upgrade spectacles? (in the Cost Recovery group). Children in the Referral groups not having received spectacles at the referral centres will receive them now, and so their visual acuity with spectacles and refractive power in each eye will be measured and recorded.

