The investigators will be using Latent class regression analysis and Finite mixture models to analyze the main outcome.

Monitoring: A dedicated Project Manager, [name], will be responsible for the overall planning, implementation, coordination, and monitoring and evaluation in the project. She will recruit a local project assistant at each site to coordinate all activities at the community level and at the base hospital and Vision Centers; ensure that appropriate planning is done for organizing and implementing screening activities; and coordinate availability of trained manpower, equipment, and facilities. [name] will interact with Orbis India Project Managers for the REACH program.

Research advisors [name], [name], and [name] each has decades of familiarity with refractive error research in children, and all have engaged in multiple research projects in India. Additionally, [name] has worked with Orbis since 2009 and is now its Director of Research.

Ethical considerations: Ethical approval has been received from two of the partners in India and Queen's University Belfast and will be sought from the additional partner. In the two Referral model groups, children who need to go to the facility to get spectacles but do not do so within the three-month period will receive free spectacles at closeout, so that no child requiring treatment will be left untreated.

Conditions

Conditions: Childhood Refractive Error

Keywords: Child, refractive error, myopia, school screening, cost effectiveness, India

Study Design: Cluster-randomised, investigator-masked trial

Study Type: Interventional

Primary Purpose: To determine the most cost-effective approach to school-based vision screening and spectacles delivery in India . Health Services Research

Study Phase: N/A

Interventional Study Model: Parallel Assignment

Randomization, Interventions: This is a cluster randomized trial, with eligible children allocated to the intervention that their school was randomized to receive. This will be one of the following three:

School Model (47 schools): Vision screening will be carried out by the vision screeners; refraction will be done at the schools by refractionists; and children who need them will be given free spectacles at the school within two weeks.

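### The itemised cost rules charge spectacle delivery to the School arm but list no delivery item for Referral, which disagrees with the plan's own promise to survey all distribution costs

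*Combined protocol and SAP*

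**What the plan says.** All references are to the combined protocol and SAP.

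- **Data to be acquired at baseline, general statement.** The program-level data are described as a "Survey of all program costs for screening and distribution for each model".
- **Same section, School rule.** The "cost will be calculated by taking the cost of the primary and secondary screening, cost of the spectacles, and cost of delivering them".
- **Same section, Referral rule.** "In the Referral model, the investigators will include the cost of primary screening, secondary screening at the vision centres and the cost of spectacles".
- **Same section, Cost Recovery rule.** It states only what is subtracted (retail price less the hospital's cost of the spectacles) and gives no base list of its own.
- **Randomization, Interventions.** In the School arm, "children who need them will be given free spectacles at the school within two weeks". In the Referral arm, "children are referred to nearby Vision Center/ secondary center for refraction and delivery of free spectacles".
- **Data Analytic Plan.** The primary analysis compares cost per child still wearing spectacles at 3 months between School and Referral. For the costs it points back to the program perspective set out earlier.
- **Sample size.** The planning inputs include "a cost of US\$1.30 per child screened in the School Model and US\$0.80 in the Referral Model". The text does not say which cost items these figures contain.

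**The concern.** The primary outcome is a ratio with program cost on top, so a cost item counted in one arm and not in the other moves the result directly. Delivery is named for School and absent for Referral, although both arms deliver spectacles.

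The general survey sentence says what will be collected; the itemised sentences say what enters the calculation. An analyst who follows the itemised rule leaves Referral distribution out, and one who follows the survey sentence keeps it in. Both could claim to follow the plan. Leaving it out can only lower the Referral cost, and Referral is the arm that the primary hypothesis expects to win.

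If the Cost Recovery arm takes over the Referral list, its comparison with School under the secondary hypothesis has the same gap.

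The planned sensitivity analysis does not close the gap. It adds family travel costs and teacher time, not the program's own cost of supplying or dispensing spectacles.

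**Working it through.** **Inputs (Sample size section).** Prevalence 3%; at least 300 children per school; 47 schools per arm; 95% of School children receive spectacles; 40% wear them in both models; cost per child screened US$1.30 (School) and US$0.80 (Referral); target referral acceptance 65%; stated break-even acceptance 58.5%.

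**1. Reproduce the plan's figure.** Cost per wearer = cost per child screened / (prevalence × receipt × wear). Prevalence and wear are the same in both arms and cancel, so

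break-even acceptance = 0.95 × 0.80 / 1.30 = 0.5846, or 58.5%. This agrees with the plan.

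**2. Planned advantage at 65%.**

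- School: 1.30 / (0.03 × 0.95 × 0.40) = US$114.04 per wearer.
- Referral: 0.80 / (0.03 × 0.65 × 0.40) = US$102.56 per wearer.
- Difference: about US$11.47, or 10% of the School figure.

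**3. Omitted cost that would erase it.** Set Referral cost per recipient equal to School: C / 0.65 = 1.30 / 0.95, so C = US$0.8895 per child screened.

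- Margin: 0.8895 − 0.80 = US$0.0895 per child screened, 11% of US$0.80.
- Per Referral recipient: 0.0895 / (0.03 × 0.65) = US$4.59, against a planned 0.80 / (0.03 × 0.65) = US$41.03.
- Whole arm: 0.0895 × 47 × 300 = about US$1,260.

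**4. Range.** The documents give no Referral delivery or dispensing cost, so the values below are assumptions. They also assume that the cost lies outside the US$0.80.

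For an omitted cost of x per child screened, true break-even = 0.95 × (0.80 + x) / 1.30, and true Referral cost per wearer at 65% = (0.80 + x) / 0.0078:

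| x (US$ per child screened) | True break-even | Referral cost per wearer at 65% (US$) |
|---|---|---|
| 0 | 58.5% | 102.56 |
| 0.02 | 59.9% | 105.13 |
| 0.05 | 62.1% | 108.97 |
| 0.0895 | 65.0% | 114.04 |
| 0.10 | 65.8% | 115.38 |

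For an omitted cost of d per recipient, the total grows with acceptance, so true break-even = 0.80 / (1.30/0.95 − 0.03d). US$1 gives 59.8%, US$2 gives 61.1%, US$3 gives 62.6% and US$4.59 gives 65.0%.

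**5. If the US$0.80 already includes Referral delivery.** The planning arithmetic then stands, but the itemised rule measures something narrower than the figure used to plan the trial. The analysed Referral cost would fall below its full program cost by the omitted amount. The wording needs correcting in either case.

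**The case against.** The strongest reply is that the survey sentence governs. It covers distribution in every model, so the plan already intends to capture Referral distribution, and the shorter itemised sentence is loose drafting. This stands in part: the documents show no decision to exclude the cost. But the survey sentence governs collection, and the sentences that define the calculation still differ by arm.

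The second reply is that the lists may reflect a real difference. School spectacles must be taken to the school, whereas Referral families collect theirs at the facility, and their journey is a family cost that is sampled separately. A separate program delivery cost in Referral may therefore be small, or sit within the facility or spectacle cost. That is fair, and it is why no size can be claimed. But the documents do not say that the cost is zero.

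Three stronger readings are tempting and are not supported:

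- **That the primary contrast is biased toward Referral.** The documents support only the direction, and only if the itemised rule is applied and the cost is not zero. Nothing in them suggests that it approaches US$4.59 per recipient.
- **That refraction at secondary centres is left uncosted.** The refraction step is costed as secondary screening; only the site is unnamed. The Population paragraph describes "Vision Centers, which will serve as the principle eye care facilities in the study", so principal rather than sole sites, and facility terms vary throughout. This is a gap in site wording.
- **That the two Referral arms use different facilities, which would confound their comparison.** The Cost Recovery description reads "children referred to Vision Center for refraction and delivery of spectacles with an option to purchase" and does not mention a secondary centre. But the background says that the cost model builds on the Referral model, the follow-up section treats the Referral groups alike, and nothing restricts Cost Recovery children to fewer facilities.

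**Conclusion.** The concern holds as an inconsistency that bears on the primary outcome. The itemised rules count delivery for School and not for Referral, although delivery is part of the Referral intervention and the same section promises distribution costs for every model. Applied literally, the rule can understate Referral cost and so favour Referral.

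The size of any understatement is unknown and may be small. What can be given is a tolerance: at 65% acceptance with equal 40% wear, the planned advantage survives an omitted Referral cost of up to about US$0.09 per child screened, or US$4.59 per recipient. This rests on the sample-size inputs and on the cost lying outside the US$0.80, which the documents do not settle.

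**What to change.** Under Data to be acquired at baseline, replace the arm-specific cost sentences with one list for all three arms:

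1. primary screening;
2. refraction, at whichever facility is used;
3. spectacles;
4. delivery and dispensing.

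Enter an explicit zero where an item does not arise in an arm, and fill the list from the program cost survey already planned. Subtract the upgrade-spectacle margin in the Cost Recovery arm only. State in the Sample size section which of these items the US$1.30 and US$0.80 contain.

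The cost is a few lines of protocol wording and, at most, one or two extra lines in the survey. The downside is that the Referral cost figure may become slightly less favourable. Fix the list before any costs are compared between arms.
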